### **Statistical Analysis**

The data was subjected to statistical analysis using:

- a) Wilcoxon signed rank test for intragroup comparison
- b) Mann-Whitney U- test for inter-group comparison

The level of significance was set at the probability value  $p \leq 0.05$ .

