Probiotics have been documented to exert several actions on a wide variety of immune cells shifting it towards the anti-inflammatory pathway [12]. Probiotics modulate mucosal immune mechanism by reducing production of pro-inflammatory cytokines through actions on NFκB pathways, increasing production of anti-inflammatory cytokines such as IL-10 and host defense peptides such as b-defensin, enhancing IgA defenses, influencing dendritic cell maturation and stimulating the activity of Treg lymphocytes [13-15]. Additionally, probiotic action could be augmented by using prebiotics such as inulin. This combination is known as symbiotic [15].

According to our understanding to the mechanism of probiotics in modulating the local and systemic inflammatory immune process and previous studies [16], it is feasible to investigate the effects of this therapy on RAS. Hence; it is one of the conditions that immune mechanism is

implicated. To the best of our knowledge, no study has been conducted in pediatric population. The aim of this study is to explore the effectiveness of lozenges containing *Lactobacillus acidophilus* (*L. acidophilus*) and *Bifidobacterium lactis*, plus inulin in the treatment of minor RAS in adult and pediatric RAS patients.

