### ***Randomization and treatment groups***

We performed power analysis to calculate minimum number of patients for the study. To achieve a significance level (type 1 error) as 0.05 and power (type 2 error) as 0.8, we decided to include 30 patients for each subgroup estimating a dropout rate of 20%. Hence, sixty adult (group A) and 60 children patients (group B) with diagnosis of minor RAS were included in the study. Each group was divided into two subgroups as follows:

Group AI: ChocBalls (*L. acidophilus* containing lozenges, PharmaCare Europe Ltd; [name])

Group AII: (control) Oracure oral gel (15 gm, Amun pharmaceutical company, Egypt)

Group BI: ChocBalls (*L. acidophilus* containing lozenges, PharmaCare Europe Ltd; [name])

Group BII: (control) Oracure oral gel (15 gm, Amun pharmaceutical company, Egypt)

The inclusion criteria for group A is as follows: 1. Males and females aged 18–45 years old, 2. Patients presenting with RAS with the following characteristics: a. Minor aphthous ulcers less than 48 hours' duration prior to enrolment, b. Size no greater than 10 mm in diameter, c. A history that ulcers normally more than 5 days to resolve without treatment. The inclusion criteria for group B is the same except age, children with RAS aged between 3 and 12 years were recruited for the study. The exclusion criteria are as follows: A known history of hypersensitivities, immunologic or systemic diseases, pregnancy, smoking, treatment with systemic steroid or other immunomodulatory agents within 1 month before the study, use of nonsteroidal anti-inflammatory drugs or oral antihistamines within 1 month prior to the study, treatment of the ulcer with any preparation or medication within 72 hours prior to the study, treatment with systemic antibiotics within 2 weeks prior to the study and a history of

adverse reactions to lactose or fermented milk products. Children with a positive family history of RAS were excluded. The nutritional status of the children was evaluated.

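### Within-arm Wilcoxon tests stand beside the randomised comparison with no stated role, and no between-arm estimate or confidence interval is planned

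*Combined protocol and SAP*

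**What the plan says.** The Statistical Analysis section is the whole analysis plan. It has two items, a "Wilcoxon signed rank test for intragroup comparison" and a "Mann-Whitney U- test for inter-group comparison", followed by one threshold for both: "The level of significance was set at the probability value" p ≤ 0.05. It gives neither test a role, does not call the within-arm test descriptive, and names no effect measure or interval for the comparison between arms.

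Three other places bear on this:

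- **Introduction.** "The aim of this study is to explore the effectiveness of lozenges" in adults and children. Study design describes a randomised, controlled trial.
- **Randomization and treatment groups.** Adults and children are each split between lozenge and gel. Ulcers must be under 48 hours old at entry, in patients whose ulcers usually need more than 5 days to clear untreated. Follow-up for effectiveness is at days 3 and 5.
- **Clinical outcome variables.** The effectiveness index is the percentage change from the patient's own baseline, and it is also graded on four ranks.

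**The concern.** In a randomised trial, effectiveness is the difference between lozenge and gel. The within-arm Wilcoxon test has a different null hypothesis, that nothing changes from baseline in one arm. In a condition that resolves by itself, that null can be false in both arms when the products do not differ at all. Finding one arm significant and the other not is also no test of the difference between them.

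The outcome definition adds to the risk. Because the effectiveness index is a change within the patient, a significant within-arm fall could be reported as effectiveness without departing from the written plan. Meanwhile the comparison that does answer the question would yield only a p-value. With subgroups of this size, that p-value says little about how large a difference remains possible.

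**Working it through.** **Plan's own figure.** The plan sets the "significance level (type 1 error) as 0.05", power 0.8, and 30 patients per subgroup allowing for 20% dropout. No effect size or SD is given, so the 30 can only be solved backwards. Evaluable per arm: 30 × (1 − 0.20) = 24. A two-sided test then detects (1.960 + 0.842) × √(2/24) = 2.802 × 0.2887 = 0.81 SD. This supplies the 24 per arm used below, with 30 as the no-dropout case.

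**What the documents support on healing.** Eligibility shows that these ulcers clear untreated. An ulcer entered at under 48 hours is about 5 to 7 days old at the day 5 visit (counting baseline as day 0), close to the point at which untreated resolution may begin. How far area or pain has fallen by day 3 is not documented.

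**Illustration 1, with no true difference between arms.** Assumptions, none from the documents: baseline area log-normal (median 16 mm², log-SD 0.5); individual percentage reduction with SD 40 points, capped at 100%; the same mean in both arms; 24 per arm; two-sided 0.05; 2,000 simulated trials per row. A dash means that the figure is not reported here.

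| Mean reduction | Both arms significant | Exactly one arm significant | Mann-Whitney significant |
|---|---|---|---|
| 5% | – | 15% | – |
| 10% | – | 32% | – |
| 15% | 15% | 47% | 5.0% |
| 20% | 36% | 47% | 4.1% |
| 25% | – | 35% | – |
| 30% | – | 15% | – |
| 40% | 98% | 1.5% | 4.6% |
| 50% | – | 0% | – |

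If p is the chance that one arm is significant, the chance of exactly one is 2p(1 − p). This cannot exceed 2 × 0.5 × 0.5 = 50%, so the 47% rows are close to the worst case. By symmetry, the lozenge is the significant arm in half of these trials: about 7% to 24% for mean reductions of 5% to 30%. With 30 per arm, exactly one arm is significant in 50% of trials at a mean of 15% and 41% at 20%.

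**Illustration 2, a different model.** Normal changes with mean/SD ratio dz, equal in both arms, 24 per arm, 4,000 trials per row.

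| dz | A given arm significant | At least one arm | Exactly one arm | Mann-Whitney |
|---|---|---|---|---|
| 0.25 | 21% | 37% | 33% | 4.7% |
| 0.5 | 63% | 86% | 46% | 4.6% |
| 0.75 | 93% | 99.5% | 13% | 5.3% |
| 1.0 | 99.7% | 100% | 0.8% | 4.6% |

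The two models agree. The within-arm results depend on how much healing occurs, while the randomised test holds its level.

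**Precision of the comparison that matters.** The half-width of the 95% interval for a difference in means, in SD units, is t × √(2/n):

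- n = 24: 2.013 × 0.2887 = 0.58 SD
- n = 30: 2.002 × 0.2582 = 0.52 SD

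A non-significant result has an interval that contains zero. An interval 2 × 0.58 = 1.16 SD wide that contains zero must reach at least 0.58 SD in one direction. The p-value alone does not show which direction, or how far.

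**The case against.** The strongest reply is that misuse is inferred. A reader might infer that the sponsor intends to claim effectiveness from within-arm p-values, or that listing the Wilcoxon test first gives it priority. The documents support neither: no section says that a within-arm result will carry the conclusion, and the order of two list items shows nothing. A valid randomised test is planned. That stands, and the point is therefore limited to roles left unstated and an estimate not planned.

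A reader might also infer that a fall by day 3 is certain in every arm, or that the Wilcoxon test measures only natural healing. Neither follows. A history of more than 5 days to clear is compatible with little change by day 3, and the control is itself a product, so within-arm change is a mixture in both arms.

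The simulated rates are also open to challenge. Neither the SD of 40 points nor any mean reduction is in the documents, and a rate near 47% should not be read as the expected one. Nor can the number of within-arm tests be set against the number of between-arm tests, because the plan does not say which outcomes and visits each test covers.

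Finally, labelling the Wilcoxon tests descriptive would remove most of the inferential problem without deleting them. That is fair, but a p-value shown beside the randomised result still invites comparison of the two, and the median and IQR describe the change better.

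**Conclusion.** The point holds in limited form, as a change that should be made rather than a fatal flaw. The plan puts a test that cannot compare lozenge with gel at the same threshold as one that can, leaves open which decides effectiveness, and gives the valid comparison no estimate or interval. These facts, and the eligibility wording that the ulcers resolve untreated, come from the documents.

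The size is illustrative and rests on the assumed healing and SD. The precision figures need only the planned subgroup size, the 20% dropout allowance and the usual formula for two means, which serves here as a guide to the precision of a rank-based interval.

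**What to change.** In the Statistical Analysis section:

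1. State that conclusions on effectiveness rest only on lozenge versus gel, separately in adults and in children.
2. Show within-arm change descriptively (median and IQR at days 3 and 5), without p-values.
3. For ulcer area, VAS pain and the continuous effectiveness index, report the Hodges-Lehmann difference with its 95% confidence interval beside each Mann-Whitney p-value.
4. For the four-rank scale, where a Hodges-Lehmann shift can take only a few values and says little, report a probability of superiority or a difference in proportions, with its 95% confidence interval.

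This costs a few sentences in the plan and a few lines of code, with no new patients, visits or data. The only loss is the within-arm p-values.

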After taking a detailed history and clinical examination, all patients eligible for study participation was assigned to the test subgroups (*L. acidophilus* containing lozenges, PharmaCare Europe Ltd; [name]) or control subgroups by using a computer-generated random number list (30 patients for each subgroup). Adult lozenge was composed of the following: *L. acidophilus* 1.5 billion cfu, *Bifidobacterium lactis* 1.5 billion cfu and inulin 0.13 g per lozenge. For children, lozenge was composed of the following: *L. acidophilus* 0.5 billion cfu, *Bifidobacterium lactis* 0.5 billion cfu and inulin 0.13 g per lozenge.

Patients were instructed to melt the *L. acidophilus* containing lozenges in the mouth slowly twice daily for 5 days (day 1 to day 5). The baseline parameters were taken and recorded on the day of the first visit. Effectiveness evaluations were made on the morning of day 3 visit and day 5 visit.

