### ***Clinical outcome variables:***

The index ulcer's size was measured by using a methodology described by Liu et al [17] on treatment days 0, 3 and 5. The investigators measured the maximum and minimum diameters when the ulcer has an oval shape, using a calibrated dental probe with millimeter markings. The two measurements were then be multiplied to represent the cross-sectional areas of the ulcer.

To evaluate pain, a visual analog scale (VAS) consisting of a 10-cm horizontal line between poles connoting no pain (origin) to unbearable pain was used. Subjects was told to mark the line with a vertical line at the point that best represented the present pain level of the ulcer.

The effectiveness indices (EI) of the ulcer size and pain improvement were calculated with the following formula: (V3 and V5 referring to the values measured at Day 3 visit and Day 5 visit, while V1 referring to the baseline value measured before the study entry):  $EI = [(V1 - V3 \text{ or } V5) \div V1] \times 100\%$ . The effectiveness indices were evaluated on a 4-rank scale: (1) Heal:  $EI \geq 95\%$ ; (2) Marked improvement:  $EI < 95\%$ , but  $\geq 70\%$ ; (3) Moderate improvement:  $EI < 70\%$ , but  $\geq 30\%$ ; (4) No improvement:  $EI < 30\%$ . Participants were asked to estimate the average duration of episodes during the past 6 months and the potential to reduce the outbreak frequency of RAS within the next 6 months was investigated. All clinical outcome variables are recorded by an investigator masked about the treatment modality that has been used.

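### The only between-arm test is an unadjusted Mann-Whitney test with no variable or visit named; a rank-based ANCOVA on the baseline already recorded would be more efficient if baseline predicts outcome

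*Combined protocol and SAP*

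**What the plan says.** The Statistical Analysis section has two methods: a Wilcoxon signed rank test within groups and "Mann-Whitney U- test for inter-group comparison". It names no outcome variable, visit, covariate or age group, and no effect estimate or confidence interval.

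Baseline data exist. Under Randomization and treatment groups: "The baseline parameters were taken and recorded on the day of the first visit", and "Effectiveness evaluations were made on the morning of day 3 visit and day 5 visit". Under Clinical outcome variables, ulcer size is measured on days 0, 3 and 5, and pain is marked on a 10-cm VAS. That section adds: "The effectiveness indices (EI) of the ulcer size and pain improvement were calculated with the following formula". The formula divides the change from baseline by the baseline value, for size and for pain, and the result is also cut into four ranks. Nothing says whether the Mann-Whitney test is applied to raw values, EI or the ranks.

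On size: "we decided to include 30 patients for each subgroup estimating a dropout rate of 20" percent, with adults and children each split into two arms.

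**The concern.** The plan collects the covariate most likely to predict the outcome and then either leaves it out of the test or uses it only through a ratio. On raw day 3 or day 5 values, baseline plays no part. On EI it enters as percent change, which is not covariate adjustment: when rho is low, dividing by baseline adds noise.

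Each age group is a small two-arm trial, with about 24 evaluable patients per arm. The choice between raw values and EI can itself move power a long way, and the plan leaves that choice open. A Mann-Whitney p-value alone also gives no size of effect.

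**Working it through.** **The plan's figure.** The 30 per arm cannot be reproduced, because no endpoint, effect or SD is given. The dropout step is consistent: 30 × 0.80 = 24, and 24 / 0.80 = 30. Working back (two-sided 0.05, 80% power), 24 per arm detects by Mann-Whitney a standardised difference of (1.960 + 0.842) × √(2/24) / √(3/π) = 0.83.

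**Normal approximation at d = 0.83.** Adjusted power is Φ(2.802/√(1−rho²) − 1.960). For a change score, replace √(1−rho²) by √(2(1−rho)). All rho values are assumed.

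| rho | raw follow-up | change score | baseline-adjusted | 24/(1−rho²) |
|---|---|---|---|---|
| 0 | 80% | 51% | 80% | 24 |
| 0.3 | 80% | 66% | 84% | 26 |
| 0.5 | 80% | 80% | 90% | 32 |
| 0.7 | 80% | 95% | 98% | 47 |

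A change-type measure loses to the raw value below rho of about 0.5 and gains above it. Adjustment is never worse than either, apart from one degree of freedom.

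**Simulation** (24 per arm, two-sided 0.05, 40,000 replicates per setting, all inputs assumed). Area: log SD 0.6, baseline median 16 mm², control follow-up median 7 mm², log effect 0.5. This baseline is compatible with the entry rule "Size no greater than 10 mm in diameter", under which the product of diameters is at most 100 mm². VAS: baseline mean 6, SD 2. Follow-up VAS is near normal (control mean 4, SD 2, effect 1.5), or has many pain-free patients (control latent mean 1, about 31% v 60% at zero), or is skewed (log-normal, median 2, log SD 0.9, log effect 0.7).

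Power (%) at rho 0 / 0.3 / 0.5 / 0.7. ANCOVA is on log(area+1) for area and on the plain scale for VAS:

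| Setting | Mann-Whitney, raw | Mann-Whitney, EI | ANCOVA | Rank ANCOVA |
|---|---|---|---|---|
| Area, none healed | 78.1/78.2/78.4/78.7 | 49.2/63.9/78.3/94.3 | 79.3/83.1/89.7/97.3 | 77.8/81.2/87.5/95.9 |
| Area, 20% v 50% healed, linked to baseline | 75.6/75.7/76.2/75.6 | 63.2/72.1/79.8/89.4 | 72.0/75.2/81.2/90.6 | 75.4/78.8/85.0/93.7 |
| Area, 20% v 50% healed, independent of baseline | 44.9/45.4/44.6/44.7 | 44.9/45.6/44.8/45.0 | 52.6/53.3/53.6/54.4 | 45.0/46.1/46.4/48.1 |
| VAS, near normal | 69.5/69.0/69.1/69.1 | 56.5/67.9/78.6/90.1 | 70.9/74.2/82.1/93.1 | 69.4/72.4/79.5/91.0 |
| VAS, many pain-free | 63.1/63.5/63.0/63.3 | 61.0/65.0/67.0/69.9 | 59.8/62.7/68.5/78.9 | 63.0/66.3/72.4/83.8 |
| VAS, skewed | 72.4/72.5/72.3/72.0 | 65.0/74.7/82.4/90.5 | 63.3/66.7/72.7/82.7 | 72.1/75.7/82.4/92.9 |

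- Rank ANCOVA minus raw, where outcome depends on baseline: −0.3 to −0.1 at rho 0, about +3 at 0.3, +8 to +10 at 0.5, +17 to +22 at 0.7. The +8 comes from the no-healing area setting with diameters rounded to whole millimetres (83.3 − 75.2 = 8.1).
- Healing independent of baseline: +0.1 to +3.4.
- Rank ANCOVA minus the better of raw and EI: −0.3 to +9.1 in every area setting, and −0.3 to +5.4 for VAS apart from one value (many pain-free, rho 0.7: 83.8 − 69.9 = 13.9).
- EI minus raw, area with none healed: 49.2 − 78.1 = −28.9 at rho 0, and 94.3 − 78.7 = +15.6 at rho 0.7.
- Plain ANCOVA on VAS against raw at rho 0: −3.3 with many pain-free (−4.1 in a run of 10,000 replicates) and −9.1 when skewed. Under skew it is 8 to 10 points below EI at rho 0.3 to 0.7.
- Null rejection of rank ANCOVA was 4.8 to 5.4%.

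**Precision.** With an assumed VAS SD of 2 cm, the 95% CI half-width is 2.014 × 2 × √(2/24) × √(1−rho²) = 1.16, 1.11, 1.01 and 0.83 cm at rho 0, 0.3, 0.5 and 0.7.

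**The case against.** **The test is sound as it stands.** True: randomisation protects it. A reader might infer that omitting baseline biases the comparison; nothing in the documents supports that.

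**EI already uses baseline.** If EI is the variable tested, baseline is not ignored, and it would be wrong to say that the plan discards it. But the plan does not say that EI is tested, and percent change falls below raw values when rho is low. EI remains the protocol's own effectiveness measure and should still be reported.

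**The gain is unknown.** This stands. The documents give no rho, SD or effect, so an unconditional claim that adjustment gains power goes too far.

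**Ordinary ANCOVA would do for pain.** This is tempting because it gives a difference directly. But VAS starts at no pain and can pile up at zero or be skewed, and plain ANCOVA can then lose to the planned test. The area argument for ranks applies to pain as well.

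**Few ulcers will have healed by day 3.** A reader might infer this from "Minor aphthous ulcers less than 48 hours" at entry and "A history that ulcers normally more than 5 days to resolve without treatment". The history is of untreated ulcers and both arms receive a product, so the inference fails. The healed share at either visit is unknown.

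**A rank test gives no interval either.** Partly right: Mann-Whitney can be paired with a Hodges-Lehmann estimate, and the interval proposed here comes from a different model than the test. For area, the two disagreed in about 2 to 10% of simulated trials. The plan, however, specifies no estimate at all.

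**Timing.** The text is in the past tense. If outcomes have been seen by arm, changing the main test is post hoc and must be labelled so.

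**Conclusion.** The firm finding is that the between-arm test has no named variable or visit, so a second analyst could not reproduce it and power depends on an unstated choice. The efficiency finding is conditional: adjusting by rank ANCOVA costs almost nothing at rho 0 and pays increasingly as rho rises, provided that outcome depends on baseline. If healing is unrelated to baseline it adds little. Against whichever of raw and EI is better, the benefit is usually modest. These sizes rest on assumed distributions, effects and correlations, with 24 evaluable patients per arm. The change is worth making because it is cheap; it does not repair a validity fault.

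**What to change.** Separately within adults and within children:

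- Name one outcome and one visit as the main comparison. Treat the other area and VAS comparisons as supportive (2 outcomes × 2 visits × 2 age groups = 8 in all; six-month outbreak frequency is outside this count and needs its own plan).
- For both area and VAS, test by regressing the rank of the outcome on arm and the rank of its baseline.
- Alongside, report the baseline-adjusted difference in VAS and in log(area+1), each with a 95% CI. State beforehand that the rank test decides if they disagree.
- Keep Mann-Whitney, with variable and visit named, as a sensitivity analysis. Still report EI and its four ranks as defined.
- Base effectiveness conclusions on the between-arm comparison, not on within-arm Wilcoxon p-values.
- If outcome data have been seen by arm, label the adjusted analysis as added afterwards.

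Cost: wording and minor programming, no new data. Statistical downsides: up to about 0.5 points of power if rho is near 0; about 2 points less than plain ANCOVA if VAS is near normal; 1 to 2 points less than log-scale ANCOVA for area if no ulcer has healed; 3 to 8 points less than a log(area+1) analysis if healing is independent of baseline. The log(area+1) difference is also harder to interpret when many ulcers have healed.

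### No primary outcome, visit or measurement scale is named and p ≤ 0.05 applies to every between-arm test, so the design's 5% error rate is tied to no conclusion

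*Combined protocol and SAP*

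**What the plan says.** The Statistical Analysis section is short. It lists a Wilcoxon signed rank test within groups and a "Mann-Whitney U- test for inter-group comparison", and then: "The level of significance was set at the probability value" p ≤ 0.05. It attaches neither test to an outcome, a visit or a scale, and does not state sidedness.

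Randomization and treatment groups gives the design error rates ("To achieve a significance level (type 1 error) as 0.05 and power (type 2 error) as 0.8") and the size: "we decided to include 30 patients for each subgroup estimating a dropout rate of 20"%. Adults and children each have their own control arm: "Hence, sixty adult (group A) and 60 children patients (group B) with diagnosis of minor RAS were included in the study". No endpoint, effect size or standard deviation accompanies the power statement. The same section fixes two post-baseline assessments without ranking them: "Effectiveness evaluations were made on the morning of day 3 visit and day 5 visit".

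Clinical outcome variables puts index-ulcer size and pain on an equal footing. It then defines effectiveness indices (EI) "of the ulcer size and pain improvement were calculated with the following formula", and adds that "The effectiveness indices were evaluated on a 4-rank scale". A 6-month outbreak outcome is also listed. Nothing in the document designates a primary outcome, a deciding visit, a testing order or a multiplicity adjustment.

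**The concern.** A type 1 error of 0.05 has meaning only for a stated test or family of tests. Here it is used to justify the sample size and then applied to every comparison. In an age group with no true difference, one chance result (day-3 pain in children, say) could be reported as effectiveness, and the plan gives a reader no basis for discounting it.

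The open choice of scale adds to the problem. EI divides the change by the baseline value, so a Mann-Whitney test on EI is a different test from one on the raw value, and the four EI ranks give a third. The plan does not say which is compared between arms.

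**Working it through.** **Inputs from the document:** threshold 0.05; two outcomes (size, pain); two visits (day 3, day 5); two age groups; 30 per subgroup with 20% dropout.

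**Assumptions:** two-sided tests; one between-arm test per outcome and visit, so 2 × 2 = 4 per age group; and the correlations between test statistics.

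**The plan's own figure.** 24 / (1 − 0.20) = 30, so 30 per subgroup fits 24 completers. At two-sided 0.05 and power 0.80 that implies a standardised difference of (1.960 + 0.842) × √(2/24) = 0.81. With no effect size, standard deviation or endpoint stated, the 30 can be neither reproduced nor refuted, and it cannot be assigned to any one of the four tests.

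**Four tests per age group, independent.** 1 − 0.95⁴ = 0.185. The exact two-sided Mann-Whitney size without ties is 0.0483 at 24 per arm and 0.0496 at 30, which gives 0.180 and 0.184.

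**Four tests, correlated.** Simulated null normal statistics, with correlation set as visit × outcome:

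| Visit / outcome correlation (assumed) | At least one p ≤ 0.05, either direction |
|---|---|
| 0.5 / 0.3 | 16.9% |
| 0.7 / 0.5 | 14.9% |
| 0.8 / 0.6 | 13.4% |
| 0.9 / 0.7 | 11.6% |
| 0.9 / 0.9 | 9.8% |
| 0.95 / 0.9 | 9.0% |
| perfect | 5% |

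Counting only results that favour the lozenge (nominal 2.5%), the first four rows apart from 0.7/0.5 give 8.5%, 6.7% and 5.8%. If the 0.05 were meant as one-sided, the range from 0.5/0.3 to 0.9/0.7 would be about 16.0% down to 10.8%.

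**If raw values and EI were both tested (eight tests).** With EI treated as log change from baseline and baseline correlation assumed at 0.3–0.7, the rate is about 19–30% between 0.9/0.7 and 0.5/0.3, and about 15–18% at the two still higher correlation settings.

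**Does Holm over four suffice once data have been seen?** Under the same model, suppose raw values or EI can be chosen afterwards and Holm is applied to the chosen four. The chance of a false positive on at least one scale is 5.7–8.9% per age group between 0.9/0.7 and 0.5/0.3. Holm over all eight gives 3.0–4.6%. Only at about 0.9/0.9 and above does the four-test version come back to about 5%.

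**Error after the fix.** One primary at 0.05 gives 5% per age group, and 1 − 0.95² = 9.75% that at least one age group is falsely positive. At 0.025 each, the trial-wide figure is 1 − 0.975² = 4.9%.

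**The case against.** The strongest defence is that the Introduction describes the aim as exploring effectiveness, and no passage says that any single p ≤ 0.05 will be claimed as proof. On that reading there is no family of confirmatory tests to control. Part of this stands: an explicit exploratory label would resolve the point. But the document also sizes each subgroup for a type 1 error of 0.05 and power of 0.8 and sets a significance threshold, so results will be read as tests unless it says otherwise.

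It is also fair to object that both the test count and the correlations are supplied by the reviewer. For that reason the range is given as about 9–17%, with 18.5% as the independent case and 5% as the floor, and not as one figure.

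A reader might infer three stronger things that the documents do not support:

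- **That eight tests per age group are planned.** Nothing says raw values and EI will both be compared, and EI, as the named effectiveness measure, may be the only scale intended.
- **That the plan accepts a trial-wide error of about one third.** 1 − 0.95⁸ = 33.7% applies only if adults and children form one family and all tests are independent. The plan states no trial-wide claim.
- **That outcome data have certainly been seen.** The methods are largely in the past tense, which suggests it, but the tense is mixed and the document does not say.

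**Conclusion.** The point holds. The plan designates no deciding comparison, and the 0.05 used for sizing is attached to no conclusion. That defect does not depend on any simulation.

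Its size does depend on assumptions. With four two-sided tests per age group, the chance of at least one false positive is above 5% unless the tests are perfectly correlated: about 9–17% under moderate to very high correlation, and 18.5% at independence. Testing both scales would raise it to about 19–30% on the main correlation grid, but this is a risk left open by the wording and not a stated intention.

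**What to change.** Begin by stating in Statistical Analysis whether outcome data have been seen.

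**If they have not:**

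- Name one primary between-arm comparison per age group, including its scale and visit. One example is the EI percentage for index-ulcer size at day 5, by two-sided Mann-Whitney at 0.05. Size is measured by the masked investigator, every enrolled patient has an ulcer so the baseline divisor is above zero, and day 5 is the last effectiveness visit. Any other single choice made in advance would also serve.
- Test the remaining outcome and visit combinations only after the primary is significant, in a stated fixed order or by Holm.
- Report EI ranks, the 6-month outcome and the within-group Wilcoxon tests as supportive.
- Say whether 5% applies per age group (0.05 each) or to the whole trial (0.025 each).
- In Randomization and treatment groups, tie the power statement to the primary test.

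**If they have been seen:** do not choose a primary or a scale now. Either apply Holm across all eight candidate comparisons per age group (raw and EI, two outcomes, two visits; smallest p against 0.05/8 = 0.00625), or across all 16 for a trial-wide claim (0.05/16 = 0.003125), with EI ranks and other outcomes supportive. Or label all results exploratory, in line with the Introduction, with no effectiveness claim.

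**Cost.** This is a cheap improvement: wording in two sections and no extra recruitment. Some p-values below 0.05 can no longer be claimed, and power falls for every test except a primary kept at 0.05. If a test alone has power 0.80 at two-sided 0.05 (an assumption, since the plan names no endpoint), its power at a stricter level is Φ(2.802 − critical value):

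- at 0.025: Φ(2.802 − 2.241) = 0.71
- at 0.00625: Φ(2.802 − 2.734) = 0.53
- at 0.003125: Φ(2.802 − 2.955) = 0.44

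The last two are for the first Holm step. Holm does somewhat better when several effects are real. The loss should be stated in the plan.
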